### III. SUBJECT SELECTION

**III.a. Field Trial inclusion/exclusion criteria:** Potential participants will be employed older health care workers (aged 50-65 years) who work a minimum of 4 night shifts (8-h) per month. The participants must have the willingness and ability to comply with the work and sleep intervention schedule, including: a) must report an ability to work three successive 8-h night shifts during two weeks; and b) must report an ability to spend 8 consecutive hours in bed attempting to sleep prior to the final two successive night shifts in the second study week. This means that individuals with a second job, child or elder care responsibilities, classes, or other non-optimal activities that would interfere with their ability to remain in bed attempting to sleep if randomized to an 8-h sleep group will be excluded. In addition, potential participants regularly taking prescription or over-the-counter medication(s) known to affect sleep [e.g., hypnotics] or alertness [e.g., antihistamines] will be excluded. In order that the participants are able to comply with the timing and duration of the 8-h afternoon-evening sleep intervention, they must have a typical commute time between their home and place of work of less than one hour.

**III.b. Field Trial Source of subjects and recruitment methods:** We will recruit up to 200 health care workers who regularly work 8-h night shifts to take part in the Field Trial in order to have up to 100 health care workers complete the entire Field Trial. We will recruit health care workers from hospitals as well as through the Massachusetts Nursing Association. We will use flyers, advertisements on websites and in newsletters, emails, internet posts, and postings on the MNA Facebook page. We will also use snowball sampling where participants may notify their coworkers.

We have selected health care workers as the occupational group in which to field test the sleep timing intervention because: (1) a large proportion of the health care workers population works night shifts; (2) night shift work has a negative impact on the safety and health of both health care workers and their patients; (3) more than half of US nurses are over age 50; (4) our prior experience has shown that health care workers are willing and valuable participants in research related to sleep and shift work; and (5) there is a large health care workers population in the surrounding community.

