#### **IV. SUBJECT ENROLLMENT**

**IV.a. Methods of enrollment, procedures randomization.** After completing the Shift Worker Survey, participants will be asked if they are a health care worker. If they are, they will be informed that they can complete an additional Health Care Worker Questionnaire and following that they may be eligible for the Field Study. They will have the option of completing the Health Care Worker Questionnaire at the same time or logging on later to complete it. Individuals who complete both surveys and who meet the inclusion/exclusion criteria will be informed within the survey that they are eligible for the Field Study. If they indicate that they want more information, they will be provided with a description of the Field Study and the Consent Form, as well as contact information for our study recruiter. We will also ask them to provide us their contact information if they wish to be contacted about the study. The potential Field Study participant will be scheduled for a consent visit during which a member of the study team will review the study, equipment, and requirements. At the end of that visit the dates for the study will be decided, based on the participant's schedule of night shifts. As described below, randomization into one of three groups will be done during the study Intervention Week.

**IV.b. Procedures for obtaining informed consent** Participants in the Field Trial will provide written informed consent in person or remotely by secured video conference or phone. When remotely, subjects will sign the informed consent form using RedCAP informed consent module prior to enrolling in the study. One of the co-investigators or the Post-Doctoral Research Fellow will explain details of the study procedures including the randomization process, study duration, baseline and intervention block data collection process, and then obtain consent from each participant before the study begins.

Informed consent for the Shift Worker Survey was waived by the Partners Human Research Committee in their initial review. Participants will be given a statement about the research based on the Partners Human Research Committee "Informed Consent in Online Research" guidelines in the beginning of the REDCap survey.

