#### **IV.c. treatment assignment and randomization.**

The field trial will use a randomized control trial design, where each participant will be randomized individually. Due to the anticipated small number of male participants, we will randomize by gender to ensure equal representation in each of the three intervention groups. The participants will be randomized to one of the 3 groups (at least 25 participants/group): A) control group (ad lib sleep); B) 8-h afternoon-evening sleep timing group; C) 8-h free sleep group.

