The Intervention Block is similar to the Baseline Block, consisting of at least three consecutive 8-h night shifts, with the participants wearing an activity monitor, maintaining a daily sleep e-diary, and rating alertness, mood and attention three times per night shift using a mini iPad provided by the investigators. At the end of the first night shift, the participant will be told about their randomization group. In the control group (Group A), participants will not be given any instructions about the timing or duration of their sleep, but will be instructed to follow their usual night shift sleep routine. In the 8-h afternoon-evening sleep intervention group (Group B), participants will be instructed to go to bed between 13:00 and 14:00 (depending on their individual commute time) and to remain in bed attempting to sleep for 8 hours (until 21:00-22:00) before the next two night shifts. In the 8-h free sleep group (Group C), participants will be instructed to remain in bed for 8 continuous hours before the next two night shifts, but will not be given any instruction regarding which 8 hours they should sleep. Immediately following the last night shift, the participant will have the option to take a saliva sample to measure their stress level (cortisol), and they will complete a follow-up questionnaire where their fatigue, recovery, stress, and quality of life will be reassessed to investigate any exploratory short-term changes resulting from the intervention schedule. After completion of the two blocks, the participant will send back the activity monitor and iPad in a prepaid secured return package by mail or an investigator will arrange to meet with the participant to retrieve the activity monitor, iPad, and cortisol sample. Within 3 months after completion of the study blocks the participant will be invited to take part in a virtual Focus Group by secure videoconferencing (via HIPAA-compliant & MGB-approved Zoom).

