## VI. BIOSTATISTICAL ANALYSIS

### VI. a) Data variables, b) Study endpoints, c) Statistical methods

**Analysis of objective sleep duration and quality, and subjective sleep quality in the Field Trial.** Sleep data will be calculated in all participants from both blocks (Baseline vs. Intervention) using actigraphy. Duration of sleep (total sleep time, TST), number of awakenings, fragmentation index (FI) during the major sleep episode and subjective sleep quality from the e-diaries may be used as outcome measures to address Aim 1. After descriptive analyses, we may use linear and generalized linear mixed models to analyze main and interaction effects for factors condition (randomization group: ad lib sleep, 8-h afternoon-evening sleep, or 8-h free sleep) and shift (Baseline: B-Night 2, B-Night 3; Intervention: I-Night 2, I-Night 3). To account for inter-individual differences, we may incorporate into our statistical model a random intercept statement allowing for means to vary between participants. We will compare within subjects (shift) and between groups (condition).

**Field Trial analysis of performance and subjective alertness (Aim 2).** Each of the tests will be administered using an iPad app. Initial processing of tests will be calculated automatically (e.g., exact time of administration, scoring of alertness scales; mean and median reaction time; number of lapses, shortest (fastest 10%) and longest (slowest 10%) reaction times on PVT]. Following the descriptive measures, analyses of RT and lapses and subjective alertness data may be performed using linear and generalized linear mixed models to analyze main and interaction effects for factors condition (randomization group, as above) and shift (as above) with participant as a random effect.

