**Exploratory analysis of subjective stress and fatigue, recovery, mood, quality of life, and physiological stress in the Field Trial (Aim 2a).** Scores of acute subjective fatigue, inter-shift recovery, subjective stress, and quality of life will be calculated from the questionnaire administered at the end of Baseline and the end of Intervention. Mood will be assessed from visual analog scales administered three times per shift on nights 2 and 3 in the Baseline and Intervention blocks. Physiological stress will be assessed by analyzing cortisol levels in the optional saliva samples collected immediately after the third night shift in the Baseline and Intervention blocks. We will compare data from the Baseline to data from the Intervention for the three groups using linear and generalized linear mixed model analysis with factors condition (randomization group) and block (Baseline or Intervention) and incorporating a random intercept statement allowing for means to vary between participants.

**Field Trial exploratory analysis of scheduled 8-h afternoon-evening sleep vs. 8-h free sleep (Aim 2b).** We may compare results described above (sleep, performance and alertness, subjective stress, fatigue, recovery, mood, quality of life, and physiological stress) between the two scheduled sleep groups to determine whether the timing of an 8-h sleep episode has a significant impact on any of the outcomes. For this analysis, data from the 8-h free sleep group will first be examined for the time of day at which it occurred. Those participants who self-selected an afternoon-evening sleep episode will be classified with the 8-h afternoon-evening sleep group. We will carry out the analyses described above using linear mixed model analysis with factors condition (randomization group) and block (Baseline or Intervention) or night, incorporating a random intercept statement allowing for means to vary between participants.

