#### **VI.d. Power analysis**

For the Field Trial we plan to enroll up to 100 participants, with at least 25 participants per group for three groups including A) control group (ad lib sleep); B) 8-h afternoon-evening sleep timing group; C) 8-h free sleep group. For the Shift Worker Survey, we aim to enroll up to 1,000 participants. In the Focus Groups we plan to enroll up to 60 participants, ~30 participants who complete the Field Trial and ~30 participants who complete the Shift Worker Survey.

Our sample size calculations for the Field Trial are based on the preliminary data from our laboratory study (6) comparing the ad lib sleep group with the 8-h scheduled afternoon-evening sleep group, and using total sleep time (TST) and Fragmentation Index (FI) after 2 nights as the outcome measures of interest. For TST, 25 participants per group will give us the power to detect a difference of as few as 78 minutes between groups ( $\alpha=0.05$ ,  $\beta=0.9$ , assumed  $\sigma=84.4$  min), a difference much smaller than that observed in our preliminary study ( $221.4 \pm 84.4$  vs.  $403 \pm 58.5$  min). For FI, 25 participants per group will give us the power to detect a difference of 37 in the fragmentation index (assumed  $\alpha=0.05$ ,  $\beta=0.9$ , assumed  $\sigma=39.9$ ), a smaller difference than that observed in our preliminary study ( $73.3 \pm 39.6$  vs.  $35.2 \pm 20.03$ ).

Our sample size calculations for the Shift Worker Survey are based on multivariable analysis. With at least 500 participants, we will have 90% power to detect an odds ratio of 1.51 for any continuous factor with one standard deviation difference, or 2.10 for any binary factor (yes vs. no) with a two-sized z-test at alpha=0.05 level, assuming the variance explained by other factors in the same model is 0.2.

Our sample size of 30 participants for the Focus Groups were selected to solicit qualitative information from approximately half of the Field Trial participants who were randomized to a sleep intervention, and from approximately 10% of the Shift Worker Survey participants who report being unable to adopt an 8-h sleep schedule when working night shifts.

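### The mixed models for Aims 1, 2 and 2a give each randomised group its own baseline mean, so the between-group estimates are generally less precise than baseline adjustment would make them

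*Combined protocol and SAP*

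**What the plan says.** Section VI.a–c plans linear and generalized linear mixed models for Aim 1 with randomised group, shift and their interaction, and a random intercept per participant. The levels of the second factor are "shift (Baseline: B-Night 2, B-Night 3; Intervention: I-Night 2, I-Night 3". Aim 2 (alertness and vigilance) refers back to the same factors. Aim 2a uses "factors condition (randomization group) and block (Baseline or Intervention) and incorporating a random intercept statement". The baseline-adjusted alternatives, a baseline covariate or equal baseline means across groups, appear nowhere. The plan also does not name the contrast that estimates the effect of afternoon-evening sleep against control. It says only that comparisons are made within subjects and between groups.

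On timing, section IV.a states that "randomization into one of three groups will be done during the study Intervention Week", and section V (Intervention Block) adds: "At the end of the first night shift, the participant will be told about their randomization group". Both baseline nights therefore precede allocation.

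Section VI.d is a plain two-group calculation without baseline: "25 participants per group will give us the power to detect a difference of as few as 78 minutes between groups".

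**The concern.** Because allocation follows the Baseline block, the three groups have the same true baseline mean, and any observed baseline difference is chance. A model with a free group effect and a group-by-shift interaction estimates that chance difference separately. With complete data its estimates are simply the group-by-night means. The group effect read from it is then one of two things:

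- the difference on the intervention nights, which ignores baseline; or
- the difference in change, which subtracts baseline with a slope of exactly 1.

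The random intercept does not alter this. (A group main effect averaged over all four nights would also mix in two untreated nights, and is set aside here.)

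At stake is precision in a trial with "at least 25 participants/group". Only total sleep time (TST) and fragmentation index have a power calculation, and it rests on laboratory data. Alertness, vigilance, mood, stress and cortisol have none, and the saliva samples are optional. Two baseline nights per person, or one baseline value for the once-per-block outcomes, are collected but not used to full effect.

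**Working it through.** **Inputs from section VI.d:** SD of TST 84.4 min; 25 per group; alpha 0.05; power 0.90 (printed as beta = 0.9). Two-sided testing is assumed because it reproduces the plan's figure. The between-night correlation rho is not in the documents, so 0.3, 0.5 and 0.7 are assumed. One SD is assumed for all groups and nights.

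**1. The plan's own figure.** Detectable difference = 84.4 × √(2/25) × (1.960 + 1.2816) = 23.87 × 3.2415 = 77.4 min by the normal approximation, and 79.0 min by the t distribution. The plan states 78. For fragmentation index with SD 39.9 the results are 36.6 and 37.3, against 37 stated. Both reproduce.

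**2. Variance of the group difference**, in units of 2σ²/n, for two baseline and two intervention nights with equal correlation:

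- unadjusted intervention nights: (1 + rho)/2
- change score: 1 − rho
- baseline-adjusted: (1 − rho)(1 + 3rho) / [2(1 + rho)]

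At rho 0.5 the last is 0.5 × 2.5 / 3 = 0.42. The detectable difference with 90% power is 77.4 × √variance.

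| rho | Unadjusted | Change | Adjusted | Saving vs change | Saving vs unadjusted | Detectable TST, min (unadjusted / change / adjusted) |
|---|---|---|---|---|---|---|
| 0.3 | 0.65 | 0.70 | 0.51 | 27% | 21% | 62 / 65 / 55 |
| 0.5 | 0.75 | 0.50 | 0.42 | 17% | 44% | 67 / 55 / 50 |
| 0.7 | 0.85 | 0.30 | 0.27 | 9% | 68% | 71 / 42 / 40 |

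At rho 0.5, matching 25 per group with adjustment would take 25 × 0.50/0.4167 = 30 per group with the change score, or 25 × 0.75/0.4167 = 45 with unadjusted nights. A simulation of 4,000 trials of three groups of 25, with estimated variance components, gave ratios of adjusted variance to change-score variance of 0.72, 0.85 and 0.90, and to unadjusted variance of 0.78, 0.55 and 0.32. These agree with the formulas.

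**3. Once-per-block outcomes (Aim 2a).** The adjusted variance is (1 + rho)/2 of the change-score variance and 1 − rho² of the unadjusted variance. At rho 0.5 both ratios are 0.75.

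**4. When the correlation is lower across blocks than within them.** Assume 0.5 within a block and 0.1 between blocks.

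- Unadjusted: (1 + 0.5)/2 = 0.75.
- Change score: 0.75 + 0.75 − 2 × 0.1 = 1.30.
- Covariate with its own fitted slope: 0.75 − 0.1²/0.75 = 0.74, before the small cost of estimating the slope.
- Constrained baseline means with only a random intercept: the pooled correlation is (2 × 0.5 + 4 × 0.1)/6 = 0.233, which forces a slope of 2 × 0.233/1.233 = 0.378. The true variance is 0.75 − 2 × 0.378 × 0.1 + 0.378² × 0.75 = 0.78, slightly worse than no adjustment. The model would report (1 − 0.233)(1 + 0.7)/(2 × 1.233) = 0.53, so its standard error would be too small.

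**The case against.** The strongest reply is that a valid analysis that is not maximally efficient misses no stated target. That is right. On the figures above, either contrast already detects less than 78 min (62–71 unadjusted, 42–65 change score), and the preliminary difference is 403 − 221.4 = 181.6 min. A reader might infer that the estimates are biased or the trial underpowered. The documents support neither: free baseline means add noise but do not shift the estimate, and the stated power reproduces without using baseline.

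Four further objections limit the point.

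- **The contrast is unnamed.** The largest savings apply only if baseline is ignored. Against the change score, which the planned interaction would give, they are 27%, 17% and 9% over the assumed range.
- **The model is not locked.** The wording for Aims 1 and 2 is permissive; only the exploratory Aim 2a commits to its model. This makes clarification easier, but no baseline-adjusted option is offered either.
- **The gain is not universal.** It is tempting to say that every group estimate loses precision. The gain over unadjusted nights goes to zero as the baseline-to-intervention correlation does, and the gain over the change score goes to zero as rho approaches 1. Group B is told to sleep at a set time instead of its habitual one, so a low correlation across blocks is possible.
- **The two remedies are not interchangeable.** A reader might take constrained means and a baseline covariate as equivalent and free of risk. Step 4 of the working shows otherwise when a random intercept is the only covariance term. They also differ with missing nights and in generalized linear models.

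**Conclusion.** The point holds as a loss of efficiency in the between-group estimates of Aims 1, 2 and 2a. Baseline is collected before randomisation, yet the planned models let it differ by group and never adjust for it. Under equal between-night correlation of 0.3 to 0.7, adjustment would cut variance by 9–27% against the change score and by 21–68% against unadjusted intervention nights. The stated 78-minute detectable difference is not undermined.

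The direction is secure for linear outcomes with intermediate correlation. The size rests on a correlation that the documents do not give. The figures in minutes also rest on an SD of 84.4 in every group, whereas section VI.d prints 58.5 for the afternoon-evening group in the laboratory study. Lapse counts and other generalized linear outcomes were not computed.

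**What to change.** For the between-group estimates in Aims 1 and 2, and for mood in Aim 2a, model I-Night 2 and I-Night 3 with the participant's mean of B-Night 2 and B-Night 3 for the same outcome as a covariate. For outcomes measured once per block in Aim 2a, use the single baseline value as the covariate.

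Alternatively, keep all four nights and constrain the baseline means to be equal across groups, but specify an unstructured covariance or add a participant-by-block random effect. A random intercept alone can misweight baseline and understate standard errors.

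Keep the planned within-subject comparisons of Baseline with Intervention as descriptive or secondary results. Do not carry the equal-baseline constraint into Aim 2b, where some participants are regrouped by the sleep time they chose and randomisation no longer guarantees equal means.

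The cost is a short addition to section VI.a–c and no new data. Statistically it is one degree of freedom for the covariate, or a few extra covariance parameters.

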The Baseline Block consists of a week during which participants work at least three consecutive 8-h night shifts. The three night shifts are preceded by a day off. All participants will be instructed to continue their normal routines, maintaining their habitual self-selected sleep-wake schedule. Sleep-wake and light exposure patterns will be recorded continuously using actigraphy, and a daily sleep e-diary will be filled in within the first hour after awakening from each main sleep episode. Performance (attention), alertness and mood will be rated three times on each night shift (just prior to their shift, on a break during their shift, and immediately after their shift). The purpose of this Baseline segment is to obtain measures of sleep duration and consolidation (to address Aim 1), alertness, mood, and performance (to address Aims 2, 2a and 2b) when working night shifts following their typical sleep routine. Immediately after the third night shift, an optional saliva sample will be taken to measure stress level (cortisol) and each participant will complete a baseline questionnaire covering questions related to fatigue, recovery, stress, and quality of life (to address Aim 2a). Participants will be given a specially configured mini iPad on which the E-diary, the performance test, alertness and mood rates, and fatigue, recovery, stress and quality of life questionnaire are programmed on.

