### Field Trial outcome variables

Sleep measurements including Total Sleep Time, Fragmentation Index, Wake After Sleep Onset, and Subjective Sleep Quality will be measured during the Baseline block and during the Intervention block. Sleep episodes in all participants will take place at home during off-shift times and will be recorded using wrist actigraphy and daily sleep e-diaries (which will be completed in the first hour after waking from the main sleep episode).

Subjective Alertness During both the Baseline and Intervention blocks, participants will complete an alertness task on the iPad three times per night shift: Once just before the night shift, once during their shift break, and once immediately following the night shift. The alertness assessment will consist of the Karolinska Sleepiness Scale (KSS) and a non-numeric bipolar (sleepy-alert) Visual Analog Scale (VAS).

Sustained Attention During both the Baseline and the Intervention Blocks, participants will complete a psychomotor vigilance task on the iPad three times per night shift: Once just before the night shift, once during their shift break, and once immediately following the night shift. The psychomotor vigilance task (PVT) is a 5-minute validated test of visual reaction time (RT) in which the participant is asked to maintain the fastest possible RTs to a simple visual stimulus.

Subjective Mood During both the Baseline and the Intervention Blocks, participants will complete a mood questionnaire on the Ipad three times per night shift: Once just before the night shift, once during their shift break, and once immediately following the night shift. Non-numeric bipolar (happy-sad) Visual Analogue Scales (VAS) will be used to assess subjective well-being and mood.

Fatigue, Inter-Shift Recovery, Subjective Stress and Quality of life will be assessed by questionnaire on the iPad immediately after the third night shift in the Baseline block and after the third night shift in the Intervention block (151, 152, 124).

Physiological Stress will be assessed by collecting a saliva sample immediately after the third night shift in the Baseline block and after the third night shift in the Intervention block to measure cortisol in subjects who live in the greater Boston area. Cortisol will be assayed in the Brigham Research Assay Core.

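### The Aim 2 and mood models leave out the pre-disclosure tests from the first intervention night, which could serve as a second baseline covariate; this is a missed precision gain, not a bias

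*Combined protocol and SAP*

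**What the plan says.** **Collection.** Section V (Intervention Block) has participants "rating alertness, mood and attention three times per night shift using a mini iPad provided by the investigators". Under Field Trial outcome variables the three times are given as "Once just before the night shift, once during their shift break, and once immediately following the night shift". Nothing exempts the first night, and Section VIII.a pays for these tests on three nights in each week.

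**Disclosure.** Section V states: "At the end of the first night shift, the participant will be told about their randomization group". The sleep instructions apply only before the two shifts that follow. Section IV.a adds that "randomization into one of three groups will be done during the study Intervention Week", without fixing the moment.

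**Analysis.** The Aim 1 paragraph of Section VI defines "shift (Baseline: B-Night 2, B-Night 3; Intervention: I-Night 2, I-Night 3". The Aim 2 paragraph takes this over by reference, with factors "condition (randomization group, as above) and shift (as above) with participant as a random effect". It is worded permissively: "analyses of RT and lapses and subjective alertness data may be performed using linear and generalized linear mixed models". The Aim 2a paragraph draws mood from nights 2 and 3 of each block, with factors condition and block. No covariate is named in any of these models.

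**Power.** Section VI.d covers total sleep time and fragmentation index, which are Aim 1 outcomes. It gives nothing for the sleepiness scale (KSS), the alertness visual analogue scale (VAS) or the vigilance task (PVT).

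**The concern.** The trial measures KSS, VAS, PVT and mood on I-Night 1 before participants know their group, then gives those scores no role in the stated models. They are the only pre-disclosure scores from the intervention week itself, so they may carry week-specific variation, such as workload or roster, that the Baseline Block cannot. Aim 2 is a hypothesis-testing aim with about 25 participants per group and no stated power, so precision matters. What is at stake is the width of the confidence intervals for the group contrasts, not their validity.

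**Working it through.** **1. The plan's own figure.** With n = 2(z₀.₉₇₅ + z₀.₉₀)²σ²/δ² and (1.960 + 1.282)² = 10.51:
- Total sleep time: 2 × 10.51 × 84.4² / 78² = 24.6, so 25 per group.
- Fragmentation index: 2 × 10.51 × 39.9² / 37² = 24.4, so 25 per group.

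Both reproduce (two-sided; the plan writes the 0.9 power as β). They concern Aim 1 and are unaffected by this point.

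**2. Which I-Night 1 tests are usable.** The pre-shift and break tests come before disclosure. The third test and the disclosure are both placed at the end of the shift, and their order is not stated. Two of the three tests are therefore safe.

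**3. Size of the gain.** The documents give no SD or night-to-night correlation for these outcomes, so every correlation below is an assumption. Night scores have unit variance, and the outcome is the mean of I-Nights 2 and 3.

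For equal correlation ρ between all nights:
- Change contrast (I-mean minus B-mean): 1 − ρ
- ANCOVA on the B-Night 2 and 3 mean: (1+ρ)/2 − 2ρ²/(1+ρ)
- The same plus I-Night 1: (1+ρ)/2 − 3ρ²/(1+2ρ)

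At ρ = 0.5 these are 0.500; 0.75 − 0.5/1.5 = 0.417; and 0.75 − 0.75/2 = 0.375. The last step is a fall of 1 − 0.375/0.417 = 10%.

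For unequal correlations the residual variance is v − c′S⁻¹c, where v is the outcome variance, S the covariance matrix of the two covariates and c their covariances with the outcome. With 0.6 within a week and 0.4 across weeks, v = 0.8, S = [[0.8, 0.4], [0.4, 1]] and c = (0.4, 0.6). That gives 0.8 − 0.256/0.64 = 0.400, against 0.8 − 0.16/0.8 = 0.600 without I-Night 1.

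| Assumed correlations | Change contrast | ANCOVA on B-Nights 2–3 | Plus I-Night 1 | Fall from I-Night 1 | Fall, both steps |
|---|---|---|---|---|---|
| 0.3 throughout | 0.700 | 0.512 | 0.481 | 5.9% | 31% |
| 0.5 throughout | 0.500 | 0.417 | 0.375 | 10.0% | 25% |
| 0.7 throughout | 0.300 | 0.274 | 0.238 | 13.2% | 21% |
| 0.6 same week, 0.4 across | 0.800 | 0.600 | 0.400 | 33.3% | 50% |
| 0.5, but I-Night 1 at 0.3 with all | 0.500 | 0.417 | 0.405 | 2.7% | 19% |
| 0.5, but I-Night 1 at 0.2 with all | 0.500 | 0.417 | 0.412 | 1.1% | 18% |
| 0.5, but I-Night 1 at 0.3 with I-Nights 2–3 | 0.500 | 0.417 | 0.415 | 0.4% | 17% |

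The step from change contrast to ANCOVA is a separate gain: at ρ = 0.5 it is 1 − 0.417/0.500 = 17%.

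**4. Cost of the covariate.** With 75 participants and three groups, going from one covariate to two inflates variance by (1 + 2/69)/(1 + 1/70) = 1.0145, about 1.4%. At ρ = 0.5 the net ratio is 0.900 × 1.0145 = 0.913. That is worth 25/0.913 − 25 = 2.4 participants per group. A comparison with 90% power before I-Night 1 is added would reach about 92.4% after it.

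**5. Limits.** The table treats I-Night 1 as a full night score; a mean of two tests out of three would probably do somewhat less. The algebra is for linear models and does not carry over directly to lapse counts in a generalized linear model.

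**The case against.** **The restriction to nights 2 and 3 is deliberate and sound.** It matches night position across blocks and isolates the nights that follow the assigned sleep. Night 1 comes after time off ("The three night shifts are preceded by a day off", stated for the Baseline Block, to which the Intervention Block is said to be similar), and B-Night 1 is left out too. This stands as a reason not to use Night 1 as an outcome or a matched comparator. It does not rule out a covariate: a Night 1 shift in mean that is common to all groups cancels between randomized groups, and only the correlation matters.

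**The plan already holds baseline information.** This is true: B-Nights 2 and 3 and a participant effect are in the model, so the gain from I-Night 1 is only incremental.

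**The remedy makes two changes.** This also stands. Section VI treats Baseline nights as outcome levels, so adjusting for them is itself a change, and at a correlation of 0.5 it yields more (17%) than I-Night 1 does (10%). The two parts should be credited separately.

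**The gain may vanish.** In the last two rows of the table it is below the 1.4% cost of the covariate. Missing I-Night 1 tests could also drop participants whom the planned mixed model would keep.

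**Stronger readings to avoid.** A reader might infer that omitting I-Night 1 biases Aim 2, that Aim 2 lacks baseline adjustment, or that all three I-Night 1 tests are clean and the gain is free. The documents support none of these. The contrast is between randomized groups with matched pre-intervention nights, the order of the third test and disclosure is open, and the covariate has a cost.

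**Conclusion.** The point holds as an optional improvement. The I-Night 1 pre-shift and break scores are collected before disclosure, are valid covariates, and have no role in the stated Aim 2 and mood models. No error or bias follows from that.

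Beyond adjustment for B-Nights 2 and 3, the expected fall in residual variance is about 6 to 13% under equal correlations of 0.3 to 0.7. It is about a third only if same-week nights are clearly more alike, which nothing in the documents establishes, and about 0 to 3% if Night 1 is atypical. Against the change contrast, both steps together give 17 to 50% in the cases tabulated. That comparison reads the planned analysis as the baseline-to-intervention interaction, which the plan does not name as its primary contrast. Every size rests on assumed correlations.

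**What to change.** For PVT measures, KSS, alertness VAS and mood VAS, prespecify a mixed model for I-Nights 2 and 3 with condition, night and a participant random intercept. Adjust it for two covariates: the mean of B-Nights 2 and 3, and the mean of the I-Night 1 pre-shift and break scores. Use the generalized linear counterpart for lapses. Leave out the I-Night 1 post-shift test, because the plan does not place it before disclosure.

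State a missing-covariate rule so that no participant is lost. One option is mean imputation of the baseline covariate. Another is a constrained longitudinal model that takes all pre-disclosure nights as outcomes with equal group means. In that model the covariance should allow same-week and cross-week correlations to differ, since a random intercept alone forces them to be equal.

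The cost is a few sentences in Section VI, 1 df for the I-Night 1 covariate (about 1.4% at 75 participants) and the handling of missing I-Night 1 tests. No new data are needed and conduct does not change. The choice should be fixed before unblinded data are examined.
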